11.5 Patient Reported Outcomes

PRO assessments will be analyzed to determine if therapeutic response and/or side effects of therapy are accompanied by measurable changes in the PROs. These responses will be summarized with descriptive statistics.

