8.0 TREATMENT COMPLIANCE

8.1 Assessment of Treatment Compliance

A member of the study team will contact subjects at 1-2 weeks and 1 month (+/- 1 week) after baseline VRP instruction to assess adherence to the program, to remind the subject to log adherence to the VRP, to remind the subjects to document when they take their AI, to answer any questions regarding the program, and to offer any additional instructions regarding the program. The preferred contact will be phone-based.

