9.5 Adverse Device Effects

Adverse Device Effects will be reported by the subject or investigator for the duration of the study. Unanticipated adverse device effects will be reported to the appropriate regulatory agencies per section 15.

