11.0 STATISTICAL METHODS

All statistical analyses will be done by the study biostatistician. A general description of the statistical methods to be used to analyze the efficacy and safety data is outlined below.

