14.2 Procedures

14.2.1 Adverse Device Effects

All adverse device effects and special reporting situations possibly, probably, or definitely related to the VRP, its exercises, its assessments and its instruments, whether serious or non-serious, will be reported from the time a signed and dated informed consent is obtained until the study completion visit.

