14.2.2 Unanticipated Adverse Device Effects

Unanticipated adverse device effects, including those spontaneously reported to the investigator within 30 days after the 12-week study completion visit, must be reported per section 15.4. The PI or site co-I assume responsibility for appropriate reporting of unanticipated adverse device effects to the regulatory authorities.

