Appendix 1 – Schedule of Events

	Enrollment^a	VRP instruction visit	1 Week Post-Instruction	1 Month Post-Instruction	12-week follow-up visit^d
Informed consent	X				
Eligibility checklist	X				
Baseline demographics		X			
PRO evaluations ^b		X			X
Cytology swab	X				X
pH collection	X				X
VRP Instruction		X			
Collect VRP use logbook					X
Phone Call ^c			X	X	

- A. The enrollment and VRP instruction visit may be conducted at the same time.
- B. The PROs will be: Vaginal Symptoms Questionnaire, NIH PROMIS Global Health scale, NIH PROMIS Female Sexual Function Profile, NIH PROMIS Global Satisfaction with Sex Life scale, NIH PROMIS Anxiety 8a scale, NIH PROMIS Depression 8a scale
- C. Phone calls to assess adherence
- D. +/- 4 weeks

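### Side effects are an analysis variable in Section 11.5, and all related device effects are reportable, but no scheduled contact asks about them, so non-serious effects may be under-ascertained

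*Combined protocol and SAP*

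**What the plan says.** Three places create a need for side-effect data:

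- Section 11.0 announces that "A general description of the statistical methods to be used to analyze the efficacy and safety data is outlined below". Sections 11.1 to 11.6 then contain no safety subsection.
- Section 11.5 states that "PRO assessments will be analyzed to determine if therapeutic response and/or side effects of therapy are accompanied by measurable changes in the PROs", and adds: "These responses will be summarized with descriptive statistics". It does not say which therapy is meant.
- Section 14.2.1 covers effects possibly, probably or definitely related to the VRP, serious and non-serious alike, which "will be reported from the time a signed and dated informed consent is obtained until the study completion visit".

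On how these effects come to be known, Section 9.5 says only that "Adverse Device Effects will be reported by the subject or investigator for the duration of the study".

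The scheduled contacts have other content. Under Section 8.1 the two calls are made "to assess adherence to the program, to remind the subject to log adherence to the VRP", to prompt recording of AI intake, to answer questions and to give further instruction. The Appendix 1 footnote describes them as "Phone calls to assess adherence".

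**The concern.** A duty to report applies to what becomes known. It does not make a non-serious effect known if the woman does not mention it and nobody asks. If she has local soreness or spotting after using the wand and keeps it to herself, her record looks the same as that of a woman who had nothing.

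Two uses of the data depend on that distinction. The comparison in 11.5 would place some women with effects in the no-effect group. The cumulative toxicity information that goes to the DSMC under Section 15.3(d) could be incomplete. Tolerability data matter here because the Introduction acknowledges how little has been published on the VRP. Once the visits are over, the missing answers cannot be reliably recovered.

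**Working it through.** **Step 1. Read each scheduled item for a side-effect question.**

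| Item | Where | Written content | Side-effect question? |
|---|---|---|---|
| Call at 1-2 weeks | 3.0, 8.1, Appendix 1 | Adherence, log reminders, questions, instruction | No |
| Call at 1 month (+/- 1 week) | 3.0, 8.1, Appendix 1 | Same | No |
| Logbook | 7.3, 9.3 | VRP use, AI doses or days missed | No |
| 12-week visit (+/- 4 weeks) | 4.5, 9.4 | Logbook return, cytology, pH, PROs | No |
| Schedule of Events | Appendix 1 | Consent, eligibility, demographics, PROs, swab, pH, instruction, logbook, calls | No row |

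**Step 2. Look at the timing.** Taking 1 month as 4 weeks, the second call falls in weeks 3 to 5 and the completion visit in weeks 8 to 16. The interval between them is nominally 12 - 4 = 8 weeks, with a range of 8 - 5 = 3 to 16 - 3 = 13 weeks. No contact is scheduled in that interval, and the visit that ends it has no listed side-effect question.

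**Step 3. Check whether a scheduled instrument could serve.** The Vaginal Symptoms Questionnaire is taken at baseline and 12 weeks (9.1.3, 9.2.3, Appendix 1). It is one of the PROs whose change 11.5 sets out to explain. Used as the side-effect variable, it would be compared partly with itself. The protocol does not designate it as a measure of harm, and its items are not reproduced.

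**Step 4. Confirm what is not affected.** Section 11.2 gives n1 = 15 (stop at 1 or fewer responses), N = 25 (reject at 6 or more), a null rate of 10% and an alternative of 30%. The probability of rejecting is the sum, over stage 1 counts x from 2 to 15, of P(Bin(15, p) = x) times P(Bin(10, p) >= 6 - x). This gives 0.802 at p = 0.30 and 0.033 at p = 0.10, in line with the stated power of about 80% and within the 5% error rate. No side-effect quantity enters the calculation.

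**Step 5. Illustrate the range.** The documents give neither a true effect rate p nor a capture fraction c, so both are assumed here. With N = 25, expected recorded cases are 25 x p x c, and the chance of recording at least one is 1 - (1 - p x c)^25. Each cell gives expected cases, then that chance.

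| Assumed p | c = 100% | c = 75% | c = 50% | c = 25% |
|---|---|---|---|---|
| 5% | 1.25; 0.72 | 0.94; 0.62 | 0.62; 0.47 | 0.31; 0.27 |
| 10% | 2.5; 0.93 | 1.88; 0.86 | 1.25; 0.72 | 0.62; 0.47 |
| 20% | 5.0; 0.996 | 3.75; 0.98 | 2.5; 0.93 | 1.25; 0.72 |

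For example, at p = 20% and c = 50%, 25 x 0.20 = 5 women are expected to have an effect. Of these, 2.5 would be recorded and 2.5 would sit in the no-effect group. The table shows how the result depends on c. It does not estimate what will happen in this trial.

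**The case against.** The strongest reply is that a reporting system exists. Sections 9.5 and 14.2.1 bind the investigator as well as the subject and cover non-serious effects. Section 15.2 has each subject's results, including significant toxicities, discussed at study meetings. Section 15.4 sets out a detailed expedited route for unanticipated effects. A reader might infer that the plan relies on spontaneous reports alone, but the text does not go that far. The protocol speaks of effects "including those spontaneously reported to the investigator within 30 days after the 12-week study completion visit" only for unanticipated effects after the last visit. This part of the reply stands: there is a duty to report. What is missing is a written way of asking, and the meetings and DSMC reports review information without collecting it.

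The contacts could also bring complaints to light. The calls deal with adherence problems, which soreness might cause, and at completion the woman sees a provider and a trained clinician takes the sample. This makes it uncertain that an effect would go unrecorded. It does not make asking or recording systematic.

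A third reply is that the Introduction uses the term side effects for the AI, whereas harms from the wand are called adverse device effects. A reader might assume that 11.5 means the device, but the documents do not settle this. If the AI is meant, its side effects are not solicited by a designated item either: the logbook asks only about missed doses. The PROs may partly reflect AI effects, but they are the outcome side of the comparison. The ambiguity is a reason to define the term.

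Finally, the consequence is limited. The 11.5 analysis is descriptive, and no test or stopping rule uses it. The device is described as class I and falls under a non-significant-risk reporting scheme. All of this stands.

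**Conclusion.** The point holds in a limited form. Section 11.5 uses a side-effect variable that the protocol neither defines nor schedules for collection. The reporting expected by 14.2.1 rests on unsolicited accounts from the subject or the investigator. Non-serious device effects may therefore be under-ascertained, and an unrecorded effect cannot be told apart from an unasked question.

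A reader might go further and conclude that device harms are under-counted, or that a particular number of women will be missed. The documents do not support that. They contain no effect rate and no capture rate, and the figures in the table are assumptions. The call script, logbook form, pamphlet and case report forms are not part of the documents, so the conclusion concerns the protocol text and not what staff may ask in practice.

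The primary endpoint, the sample size and the Simon decision rules are untouched. This is a cheap improvement to safety ascertainment and to one descriptive analysis.

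**What to change.** 1. Add one standard, open adverse-device-effect question, with brief prompts (pain, bleeding, irritation, infection), to the 1-week call, the 1-month call and the 12-week visit. Record the answer each time, including a negative one.
2. Add a matching row to Appendix 1 at those three points, and refer to it from Sections 8.1, 9.4 and 9.5.
3. State in 11.5 whether therapy means the VRP or the AI. If it means the VRP, name the solicited record as the side-effect variable. If it means the AI, name the source that will be used.
4. Add a short descriptive safety summary to Section 11, so that the announcement in 11.0 is met. Give the number and percentage of women with any device effect, and keep solicited and unsolicited reports distinguishable.

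The cost is about a minute at each of three contacts that already take place, plus one short form. More minor events will be recorded. No extra visit or procedure is needed.

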10.0 MEASUREMENT OF INTERVENTION EFFECT

10.1 Response

A positive response to the VRP intervention will be confirmed if the percentage of superficial vaginal cells changes from $< 2\%$ to $\geq 4\%$ from pre-intervention to post-intervention.

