11.2 Sample Size Determination

The Simon Two Stage design will be utilized for this study. The null hypothesis that the true positive response rate is 10% will be tested against a one-sided alternative using the exact binomial test. The study will be powered to detect a positive response rate of 30% or greater with approximately 80% power and a type I error rate of 5%.

The first stage sample size will be 15 patients. If there are 1 or fewer responses in these 15 patients, the study will be terminated. If the trial goes on to the second stage, a total of 25 patients will be studied (i.e. additional 10 patients will be recruited). The null hypothesis will be rejected if 6 or more responses are observed in 25 patients. We will assess response with a blinded standardized interpretation of superficial vaginal epithelial cells by a board-certified pathologist.

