11.4 Secondary Endpoint

Changes in the vaginal pH will be analyzed to determine the extent to which the changes correlate with changes in the primary outcome and with patient reported outcomes. Given the longitudinal nature of the study, linear and generalized linear mixed effects models will be fit to the data gathered. The restricted maximum likelihood (REML) criterion will be used and 95% semi-parametrically bootstrapped confidence intervals will be obtained for all parameters. All statistical analyses will be conducted using R (R Core Team 2014).

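### Section 11.5 links PRO change to a response defined only as yes/no; the change in percentage superficial cells would keep the cytology–PRO question answerable after a stage 1 stop and usually more precise otherwise

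*Combined protocol and SAP*

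**What the plan says.** Section 11.5 sets the purpose of the PRO analysis as to "determine if therapeutic response and/or side effects of therapy are accompanied by measurable changes in the PROs", and plans descriptive statistics for it. It does not define therapeutic response there.

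Elsewhere response is always binary. Section 10.1 begins "A positive response to the VRP intervention will be confirmed if the percentage of superficial vaginal cells changes from" and gives below 2% before and at least 4% after the intervention. Sections 3.0 and 11.3 use the same 4% cut, and 11.2 counts responses for the two-stage rule: "If there are 1 or fewer responses in these 15 patients, the study will be terminated"; otherwise "a total of 25 patients will be studied".

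Section 11.4 is worded differently. It examines changes in vaginal pH for "the extent to which the changes correlate with changes in the primary outcome and with patient reported outcomes". That relates pH to cytology and pH to PROs. No section plans a direct analysis of cytology change against PRO change. Objective 2.3.2 concerns PRO change over 12 weeks in the whole population, whatever the response.

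**The concern.** The primary endpoint is a cytological marker, while the introduction gives relief of atrophy and dryness symptoms as the purpose of the programme and says that little published evidence supports either effect. Section 11.5 is the only place that asks whether cytology and symptoms move together. If its cytology variable is responder status, two things follow. After a stage 1 stop there is no usable responder group. After continuation, women just under 4% are pooled with women who did not change, and women just over 4% with those far above it, although the percentage itself is read at both visits. At stake is the precision of that association, not the primary decision or the estimate of PRO change.

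**Working it through.** **Inputs from section 11.2.** Null rate 10%, alternative 30%, 15 patients in stage 1 with a stop at 1 or fewer responses, 25 in total, rejection at 6 or more. The documents give no distribution for the cytology percentage and no expected correlation with the PROs; both are assumed below.

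**1. The plan's own design.** Exact two-stage enumeration gives a type I error of 0.0328 and power of 0.8017. This agrees with the stated 5% limit and approximately 80% power.

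**2. Chance of a stage 1 stop**, P(X ≤ 1 | n = 15):
- At 10%: 0.9^15 + 15 × 0.1 × 0.9^14 = 0.2059 + 0.3432 = 0.549.
- At 30%: 0.7^15 + 15 × 0.3 × 0.7^14 = 0.0047 + 0.0305 = 0.035.

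The split is then 0 versus 15 or 1 versus 14. With 1 versus 14, the standard error of a mean difference is √(1/1 + 1/14) = 1.04 SD, and the responder group has no variance to estimate. This step needs no distributional assumption.

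**3. Information kept by the split if the trial continues.** For a normal variable cut at upper-tail proportion p, the share kept is φ(z)² / [p(1 − p)], where z is the cut point:
- p = 0.30: 0.3477² / 0.21 = 0.576, so 42.4% is lost.
- p = 0.24 (6 of 25): 0.3109² / 0.1824 = 0.530, so 47.0% is lost.
- p = 0.36 (9 of 25): 39.2% lost.
- p = 0.50: 36.3% lost, the minimum.

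The loss passes below 40% at about 34% responders. Given continuation, the chance of 9 or more responders is 33% at a true rate of 30% and 0.1% at 10%.

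**4. Dependence on shape.** If non-responders lie between 0% and 2% and responders spread over 4% to 10%, the split loses only 13% to 16%. If cytology is lognormal and the PRO is linear in its logarithm, a correlation on the raw percentage may be no better than the split. A rank correlation is unchanged by that transformation, which is why ranks are preferred.

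**5. Illustration of precision.** Simulated bivariate normal data, n = 25, two-sided 5%. The rank correlation is compared with a two-sample t-test by responder group at 24% to 30% responders. Tied values are set at a floor.

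| True correlation | Values tied | Rank correlation | Responder split |
|---|---|---|---|
| 0.5 | none | 68–69% | 44–48% |
| 0.5 | 50% | about 60% | 44–48% |
| 0.5 | 70% | about 50% | about 48% (30% responders) |
| 0.6 | none | 86% | 61–66% |
| 0.6 | 70% | 68% | 66% (30% responders) |

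With 15 women and a correlation of 0.5, the rank correlation has about 43% power with no floor and 22% to 29% with 70% to 80% tied. These figures do not allow for a stage 1 stop itself selecting women with little movement.

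**The case against.** The strongest reply is that 11.5 does not specify the analysis criticised. It speaks of therapeutic response where 10.1 and 11.3 define a positive response; it adds side effects as an alternative; and it plans description only. A reader might infer that the plan commits to a responder versus non-responder test. It does not: the binary reading is natural, because no other definition of response exists, but it remains an inference. The powers above therefore illustrate lost precision and do not describe the failure of a planned test.

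A reader might also infer that the split always discards more than 40% of the information. That needs a normal scale and a response rate below about 34%, and neither is assured. The floor matters too: section 5.1.7 requires under 2% at entry, so many non-responders may tie near zero, and with about 70% tied the advantage nearly disappears.

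Nor is the PRO objective damaged. Objective 2.3.2 stands whatever the response, and the cytology–PRO association is not a listed objective. It is, however, the question that 11.5 itself poses.

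Finally, the limit of one responder applies to the 15 counted patients. Section 8.2 replaces non-adherent women yet still analyses them, so the analysed set could be larger and hold another responder.

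All of this narrows the point. None of it supplies a usable comparison after a stage 1 stop, or a planned direct analysis of cytology against PROs.

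**Conclusion.** The point holds in a limited form. On the only definition of response that the plan gives, the question in 11.5 cannot be answered after a stage 1 stop; that is arithmetic from the stopping rule. If the trial continues, a loss of about 42% to 47% at 30% to 24% responders rests on the normal scale. It is smaller with 9 to 16 responders in 25 or with clumped data, and many ties can remove most of the gain from the continuous value. In the simulated cases the rank correlation was about equal to the split or better. This is an inexpensive improvement worth making; it does not touch the primary test, the sample size or objective 2.3.2.

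**What to change.** In section 11.5:
- State that the cytology variable for the PRO association is each woman's change in percentage superficial cells, taken from the blinded reads of both slides.
- Report its rank correlation, corrected for ties, with the change in each PRO score, with a bootstrap 95% CI, as an estimate and not a test. This stays within a descriptive plan, and 11.4 already uses bootstrap intervals.
- Keep the responder versus non-responder summary as supportive, and say that therapeutic response there means the definition in 10.1.

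The cost is SAP wording: no new data, visits or patients. The downside is ties near the baseline floor and wide intervals, especially if only 15 women are available; report the number of tied values beside each estimate.

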11.6 Adherence to AI Therapy

Adherence to AI therapy will be recorded using a patient-reported log.

12.0 SUBJECT COMPLETION/WITHDRAWAL

12.1 Completion

A subject will be considered to have completed the study if she returns for the 12-week study completion visit.

12.2. Withdrawal From the Study

A subject will be withdrawn from the study for any of the following reasons:

- Lost to follow-up

- Withdrawal of consent (no further treatment AND no further follow-up)
- Lack of adherence to the study procedures

If a subject is lost to follow-up, every reasonable effort must be made by the study site personnel to contact the subject and determine the reason for discontinuation/withdrawal and survival status. When a subject withdraws before completing the study, the reason for withdrawal is to be documented in the study records.

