4.4 Intervention

All subjects on this study will receive the VRP intervention. Enrolled subjects will receive in-person instruction on how to perform the VRP.

The instructor is a certified sexuality counselor who has been trained in the instruction of the VRP.

The VRP consists of instructing subjects regarding digital physical therapy techniques for the vulva and vaginal introitus as well as internal physical therapy techniques using a therapeutic vibrating vaginal wand designed for the VRP and FDA-approved as a class I durable medical device (FeMani Vibrating Massage Wand). Details of the program are outlined in a brochure that will be provided to participants.

4.5 Study Completion Visit After 12 weeks (+/- 4 weeks) subjects will return to see the provider, return log books documenting adherence to prescribed therapy, have repeat vaginal cell cytology samples and pH testing, and complete post-intervention PRO surveys.

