8.2 Subject replacement

For this study, lack of adherence will be defined as < 3 days/week participation for 2 weeks or

more as assessed on the 1-month phone call. If a subject is found to be not adhering to the study protocol, a new subject will be enrolled in a 1:1 ratio. Subjects lost to follow-up for any reason will be replaced in a 1:1 ratio. All subjects enrolled and not lost to follow-up, regardless of adherence status, will have their data collected and analyzed accordingly.

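### Section 12.2 withdraws women for lack of adherence while 8.2 keeps their data; unless the two are reconciled and the Simon denominator fixed, the tested rate may become an adherent-only rate

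*Combined protocol and SAP*

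**What the plan says.** Section 12.2 is mandatory in form: "A subject will be withdrawn from the study for any of the following reasons". It lists three reasons: loss to follow-up, withdrawal of consent, and "Lack of adherence to the study procedures". It gives no threshold for the third.

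The only definition of non-adherence is in 8.2: "For this study, lack of adherence will be defined as < 3 days/week participation for 2 weeks or" more, judged at the 1-month call. Section 8.2 then provides for replacement: "If a subject is found to be not adhering to the study protocol, a new subject will be enrolled in a 1:1 ratio". On data it says: "All subjects enrolled and not lost to follow-up, regardless of adherence status, will have their data collected and analyzed accordingly".

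The post-intervention slide is taken at the completion visit. There, under 4.5, subjects "have repeat vaginal cell cytology samples and pH testing, and complete post-intervention PRO surveys". Section 12.1 ties completion to that visit: "A subject will be considered to have completed the study if she returns for the 12-week study completion visit". Appendix 1 shows no study contact between the 1-month call and the 12-week visit, and no early-termination visit.

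Section 11.2 sets the decision rule for exactly 15 and then 25 patients. Section 11 names no analysis set and does not say how a missing slide is counted.

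**The concern.** A woman judged non-adherent at one month is to be withdrawn under 12.2 and to have her data collected and analysed under 8.2. If withdrawal means that she does not attend the completion visit, she has no post-intervention slide and cannot be classified for the primary endpoint. Section 8.2 then supplies a replacement who can be.

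The trial's hypothesis is that using the VRP improves cytology, so women who do not use it are the expected non-responders. Exchanging them for other women would move the tested quantity from the rate among all enrolled women to the rate among those who kept up the programme.

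Section 12.2 also has no category for a woman who stops the VRP but remains in follow-up, and none for an adverse device effect. A woman who stops because of discomfort would fit only under lack of adherence, unless she withdraws consent. Her 12-week pH, patient-reported outcomes (PROs) and logbook could be lost with the slide.

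**Working it through.** **Inputs from 11.2.** Null rate 10%, alternative 30%, n1 = 15 (stop at 1 or fewer responses), N = 25 (reject at 6 or more), one-sided 5% type I error, about 80% power.

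**Step 1: reproduce the design.** With X1 ~ Bin(15, p) and X2 ~ Bin(10, p),

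P(reject) = Σ over x = 2 to 15 of P(X1 = x) × P(X2 ≥ 6 − x).

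- p = 0.10: 0.0328, within the 5% limit.
- p = 0.30: 0.8017, matching the stated power.

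The design is sound as written. The question is which women it is applied to.

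**Step 2: the rate tested if non-adherent women are withdrawn, replaced and not counted.** The documents give neither the non-adherent share f nor how often such women respond; both are assumed here. Let q be the response rate among adherent women and k·q the rate among non-adherent women. Holding the all-enrolled rate at 10%,

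(1 − f)q + f·k·q = 0.10, so q = 0.10 / (1 − f + f·k).

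| f | k | q | P(reject) |
|---|---|---|---|
| any | 1 (equal response) | 0.10 / 1 = 10.0% | 0.033 |
| 20% | 0.5 | 0.10 / 0.90 = 11.1% | 0.051 |
| 20% | 0 (never respond) | 0.10 / 0.80 = 12.5% | 0.082 |
| 30% | 0.5 | 0.10 / 0.85 = 11.8% | 0.064 |
| 30% | 0 | 0.10 / 0.70 = 14.3% | 0.134 |

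**Step 3: the same women kept in the count, with a missing slide scored as non-response.** For f = 20%:

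- k = 0: the counted rate is 0.80 × 12.5% = 10.0%, and P(reject) stays at 0.033.
- k = 0.5: the counted rate is 0.80 × 11.1% = 8.9%, below 10%.

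Either way there is no upward shift.

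**Step 4: follow 8.2 alone.** Non-adherent women are analysed and replacements are added, so the count passes 15 and 25, for which 11.2 gives no cut-offs. Keeping the cut-offs at 1 and 6 with a true rate of 10%:

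| Stage 1 / total | Type I error |
|---|---|
| 15/25 | 0.033 |
| 16/27 | 0.046 |
| 17/28 | 0.054 |
| 18/30 | 0.072 |
| 19/31 | 0.082 |

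The 18/30 row corresponds to 20% extra women at each point (15 × 1.2 and 25 × 1.2). Resolving the conflict in favour of 8.2, with nothing else changed, therefore raises a problem of similar size.

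**The case against.** **Study procedures may not mean VRP use.** Section 9.1 uses Study Procedures as the heading over the cytology, pH and PRO evaluations, while VRP use is treated as the intervention and its adherence as treatment compliance. On that reading 12.2 concerns women who refuse evaluations, and the sections need not collide. The reading is possible, but 12.2 supplies no definition of its own and 8.2 defines lack of adherence for the study as a whole. The point stands, as an ambiguity to be resolved.

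**Loss of the slide is not stated.** A reader might infer that a woman withdrawn for non-adherence certainly has no 12-week swab. The documents do not say so. The bar on follow-up is attached only to one reason, "Withdrawal of consent (no further treatment AND no further follow-up", and 9.4 asks all subjects to return at 12 weeks. This objection stands: the loss is the natural reading of withdrawal set against completion in 12.1, but it remains an inference.

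**Post-baseline information is not wholly lost.** A reader might infer that such a woman leaves nothing behind. In fact both adherence contacts (8.1) will have taken place, adverse device effects are reported from consent (14.2.1), and 12.2 requires the reason for withdrawal to be documented. What is at risk is the 12-week outcome data.

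**The raised rejection probability is not a false positive for an inert programme.** If the VRP does nothing, using it should not alter cytology. Both groups would then respond alike, and the error would stay at 3.3%. This too stands. The higher figures arise only where adherent women do respond more often, and they describe a change in what is estimated.

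**Conclusion.** Sections 12.2 and 8.2 conflict under the only definition of non-adherence the protocol gives, and they must be reconciled. An adherent-only rate results if three things hold: withdrawal ends participation before the completion visit, withdrawn women leave the 15/25 count, and non-adherent women respond less often. The 1:1 replacement, the fixed 15/25 rule and the absence of a missing-slide rule make the second likely; the trial's own hypothesis implies the third.

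The direction is therefore supported, but the size is not known. At an assumed 20% withdrawn and replaced, with an all-enrolled rate of 10%, the chance of rejecting is 5.1% (half the adherent rate) or 8.2% (no response), against 3.3% as designed. At half the adherent rate the excess over the nominal 5% is slight, and with equal response there is none.

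A reader might go further and conclude that the trial would wrongly declare an inactive programme effective, or that the response rate will certainly be inflated. The documents support neither. They support a correction made now, because a slide not taken at 12 weeks cannot be recovered and the result turns on six responses among 25 women.

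**What to change.** **Section 12.2.** Separate stopping or under-using the VRP from leaving the study, and remove lack of VRP adherence as a reason for study withdrawal. Ask every woman who has not withdrawn consent to attend the completion visit for cytology, pH, PROs and logbook. Record the reason for stopping the VRP, including any adverse device effect. This concerns data collection only and does not touch when a woman should stop using the device.

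**Sections 8.2 and 11.2.** Fix in advance which 15 and 25 women the Simon rule is applied to. One option is the first 15 and the first 25 enrolled regardless of adherence, with a missing slide counted as non-response. Otherwise, recompute the cut-offs for the number actually analysed. Without this step the change to 12.2 is incomplete, as the 18/30 case (7.2%) shows.

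**Cost.** A wording amendment to three sections and no new visits, since the completion visit is already scheduled for all subjects. The observed response rate may be somewhat lower, because non-adherent women would count.
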